0.1 Protocol additions

Version 2:

- Addition to participant flow (1.2.20)
- Completion of entry to ClinicalTrials.gov.

Version 3: Last updated December 26, 2022

- Addition of ClinicalTrials.gov ID (1.1)
- Addition to 'actual sample size' (1.2.14)
- Addition to 'recruitment status' (1.2.15)
- Addition of completion date (1.2.19)
- Addition to participant flow and flowchart (1.2.20)
- Additional registration to EHS-registry with addition to 'baseline characteristics' (1.2.20)
- Correction of 'adverse events' under 1.2.20 since participant previously denoted with an adverse event exhibited exclusion criteria and was not included
- Addition of 'adverse events' (1.2.20)
- Addition of 'brief summary' (1.2.20)
- Addition of 'date of posting of results summaries' (1.2.20)
- Addition to IPD sharing statement (1.2.21)
- Addition to 'contributions' (1.5)
- Addition to 'statistical analysis' (3.1.9)

1.1 Trial Registration

ClinicalTrials.gov:

- Date of Registration: June 24, 2022.
- NCT05446675

Secondary identifying number: EC/EH/220608-SK.

1.2 WHO Data Set

1.2.1 Monetary or Material Support

None.

1.2.3 Secondary Sponsors

None.

1.2.5 Public Title

Endoscopic eTEP versus Open Rives-Stoppa.

1.2.6 Scientific Title

Single-Center Observational Study with Comparison of Endoscopic Extended-View Totally Extraperitoneal Prosthesis (eTEP) Versus Open Rives-Stoppa Repair as a Treatment of Midline Abdominal Wall Hernias with Rectus Diastasis.

1.2.7 Countries of Recruitment

Belgium.

1.2.8 Health Conditions Studied

Midline abdominal wall hernias alongside rectus abdominis diastasis.

1.2.9 Interventions

Group 1 (eTEP): Patients who underwent an endoscopic repair of their midline abdominal wall hernias and rectus diastasis via the extended-view totally extraperitoneal prosthesis method within our center.

Group 2 (Rives-Stoppa, control group): Patients who underwent an open midline repair with sublay mesh according to the technique of Rives-Stoppa within our center.

1.2.10 Inclusion Criteria

Group 1 (eTEP):

- Patients who underwent an eTEP procedure in our center
- Preoperative existence of one or more midline abdominal wall hernias
- Preoperative existence of rectus abdominis diastasis

Group 2 (Rives-Stoppa, control group):

- Patients who underwent an open Rives-Stoppa (midline repair with sublay mesh) in our center

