1.2.11 Exclusion Criteria

Group 1 (eTEP):

- Preoperative absence of midline abdominal wall hernias
- Preoperative absence of rectus abdominis diastasis
- Intraoperative performance of transverse abdominis release (TAR)
- Intraoperative inguinal hernia repair

Group 2 (Rives-Stoppa, control group):

- Intraoperative performance of transverse abdominis release (TAR)
- Intraoperative performance of anterior component separation
- Intraoperative inguinal hernia repair

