1.2.12 Study Type

Single-center, observational study.

Non-randomized allocation:

- Group 1 (eTEP): First 30 patients who meet the inclusion criteria and do not exhibit any of the exclusion criteria will be investigated. The option for endoscopic eTEP repair, if feasible, is given preoperatively as a standard for the treatment of symptomatic midline abdominal wall hernias with concomitant rectus abdominis diastasis as an alternative to open Rives-Stoppa mesh repair. The modality of operative treatment is made in cooperation with the patient.
- Group 2 (Rives-Stoppa, control): Thirty patients will be selected out of all patients who underwent an open Rives-Stoppa (midline repair with sublay mesh) in our center and who do not meet any of the exclusion criteria. Patient selection will consist of matching to patients in group 1 according to gender and age (e.g. a male patient in group 1 will be matched to a male patient (group 2) out of our records

who underwent an open Rives-Stoppa repair and whose age most closely resembles the age of the matched patient in group 1).

Masking: None.

Assignment: Two-group, parallel.

Purpose: Comparing two routinely used interventions for the treatment of midline abdominal wall hernias with rectus abdominis diastasis.

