- No early recurrences were found in both groups (postoperative consultation at approximately one month after surgery).
- Bulging of the abdominal midline was seen in 11 participants in the eTEP group and was not seen in the open RS group, this difference was statistically significant.

*Comparable parameter: Types of analgesics were divided into three categories. Category 1 contained only paracetamol, category 2 contained all non-steroidal anti-inflammatory drugs, and category 3 consisted of all opioids. A combination of active substances (in one analgesic) of which at least one was an opioid was seen as category 3. For each participant the absolute amount of analgesics in each category was calculated between postoperative day one and the day before discharge, this amount was divided by the amount of days between postoperative day one and the day before discharge.

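### The study is framed as a comparison in midline hernia with rectus diastasis, but Group 2 eligibility and matching do not ensure that controls had diastasis

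*Protocol*

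**What the plan says.** Three places in the protocol set the population for both procedures.

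- Section 1.2.6 (scientific title) compares the two repairs "as a Treatment of Midline Abdominal Wall Hernias with Rectus Diastasis".
- Section 1.2.8 gives the condition studied as "Midline abdominal wall hernias alongside rectus abdominis diastasis".
- Section 1.2.12 states the purpose as "Comparing two routinely used interventions for the treatment of midline abdominal wall hernias with rectus abdominis diastasis". It also says that eTEP is offered for "symptomatic midline abdominal wall hernias with concomitant rectus abdominis diastasis as an alternative to open Rives-Stoppa mesh repair", so the choice between the techniques arises in patients who have diastasis.

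For Group 1, diastasis is an inclusion criterion (1.2.10), and section 1.2.11 excludes "Preoperative absence of rectus abdominis diastasis".

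For Group 2, the only inclusion criterion in 1.2.10 is "Patients who underwent an open Rives-Stoppa (midline repair with sublay mesh) in our center". The exclusions in 1.2.11 are transverse abdominis release, anterior component separation and inguinal hernia repair. On selection from that pool, 1.2.12 says "Patient selection will consist of matching to patients in group 1 according to gender and age".

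The objective (2.1.2) and the public title (1.2.5) name the procedures and no population.

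**The concern.** Followed as written, the plan admits controls who do not have the condition that the study says it compares treatments for. Matching on gender and age does nothing to correct this, because diastasis is not a matching variable.

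If some controls had no diastasis, a difference between groups could come from the technique, from the difference in indication, or from both. That would touch the primary outcomes (length of stay and postoperative pain management), the complications and the reported midline bulging. The protocol itself treats diastasis as relevant to the operation: in 1.2.20, two eTEP procedures were converted because the diastasis was judged too large to close endoscopically.

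At stake is whether the comparison can be read as the title and purpose invite, as eTEP against open repair in patients with diastasis.

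**Working it through.** **Step 1. Set the sections side by side.**

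| Element | Diastasis required? | Section |
|---|---|---|
| Scientific title | Yes, for both procedures | 1.2.6 |
| Condition studied | Yes | 1.2.8 |
| Purpose | Yes, for both procedures | 1.2.12 |
| Group 1 inclusion and exclusion | Yes, stated twice | 1.2.10, 1.2.11 |
| Group 2 inclusion | No | 1.2.10 |
| Group 2 exclusion | No | 1.2.11 |
| Matching of Group 2 | No; gender and age only | 1.2.12 |
| Objective, public title | Silent | 2.1.2, 1.2.5 |

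**Step 2. Look for a rule elsewhere that closes the gap.** Sections 3.1.2, 3.1.3 and 3.1.8 refer back to 1.2.9 to 1.2.12. Section 3.1.7 speaks of eligible pathology, but for Group 2 that leads back to criteria without diastasis. No section requires diastasis in controls or restricts the analysis to controls who had it.

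**Step 3. Is there a design figure to reproduce?** No. Section 1.2.14 gives 30 per group without further inputs, and this point does not depend on it.

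**Step 4. One illustration of why the missing count matters.** The input is in 1.2.20: "Bulging of the abdominal midline was seen in 11 participants in the eTEP group and was not seen in the open RS group". With 30 per group (1.2.14), and taking all 30 in each group as assessed, the table is 11/30 versus 0/30.

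Assume, and this is strong, that bulging arises only in patients who had diastasis. Controls without diastasis then carry no information on bulging, and the relevant comparison is 11/30 versus 0/m, where m is the number of controls with diastasis. The protocol does not give m, so it is varied.

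The probability of the observed table with margins fixed is C(30,11) / C(30+m,11). The two-sided Fisher p adds every table in the opposite tail that is no more probable.

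- m = 30: 54,627,300 / 342,700,125,300 = 0.000159. The opposite tail is equal by symmetry, so p = 0.0003. This agrees with the significance that the protocol reports.
- m = 15: 54,627,300 / 10,150,595,910 = 0.0054; with the opposite tail, p = 0.008.
- m = 9: 54,627,300 / 1,676,056,044 = 0.0326; with the opposite tail, p = 0.040.
- m = 8: 54,627,300 / 1,203,322,288 = 0.0454; with the opposite tail, p = 0.077.

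On this assumption, the result in the titled population depends on a number that the protocol neither fixes nor reports. Bulging is not a listed primary or secondary outcome (1.2.16, 1.2.17). For the listed outcomes, the protocol has no figures from which a size could be derived.

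**The case against.** The strongest reply is that the objective in 2.1.2 compares two procedures, and a control group defined by procedure serves that objective. This is fair as far as it goes. A reader might infer that 2.1.2 contradicts the title, but an objective that is silent on population contradicts nothing. It simply does not settle which population is meant. The mismatch is between 1.2.6, 1.2.8 and the purpose in 1.2.12 on one side and the Group 2 criteria on the other, and 2.1.2 does not remove it.

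A second reply is that nothing shows any control to have lacked diastasis. This stands. A reader might infer that the control group was in fact mixed, or that the posted results are biased in a known direction. The document supports neither. The controls' status may be in the registry, in the final report, or in the participant flowchart, which is not reproduced in the text at hand.

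Third, every eTEP patient had diastasis by criterion, so what is observed within that group does apply to patients with diastasis. That is correct. Only the between-group contrast is uncertain.

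Fourth, the illustration rests on an extreme assumption and on an outcome that was not prespecified. Both are true. The change from p = 0.040 at m = 9 to p = 0.077 at m = 8 should not be read as a threshold of safety, because it belongs to that assumption and that test.

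Finally, recruitment is complete, so eligibility cannot be changed. That limits the remedy to reporting, analysis and wording, all of which remain open: section 4.1.2 foresees supplying a final version of the protocol to the journal.

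**Conclusion.** The concern holds as a defect of definition. The scientific title, condition and purpose place both procedures in midline hernia with rectus diastasis, while Group 2 eligibility and matching do not ensure that controls had it. This follows from the text and rests on no assumption. It is a question of eligibility, which a statistical analysis plan could not alter.

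The consequence is conditional. If some controls lacked diastasis, the contrast mixes technique with indication, by an amount and in a direction that the document does not allow anyone to state. If all 30 had it, there is no confounding from this source and only the criteria are loosely worded. The bulging figures show that the count can matter (p from 0.0003 with all 30 controls to 0.077 with 8), but only on the assumption that bulging requires prior diastasis. They say nothing about length of stay or analgesia.

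This should be fixed: the remedy is cheap, and without it a reader cannot tell whether the comparison applies to the population in the title.

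**What to change.** 1. Keep the eligibility text as the record of what was done. Add to 1.2.20 the controls' preoperative diastasis status from existing records: documented present, documented absent, not documented, each as n of 30.

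2. Unless all 30 controls have documented diastasis, add to 3.1.9 a sensitivity analysis of all 30 eTEP patients against the controls with documented diastasis. Adjust for age and gender for length of stay and analgesia, and use an exact unpaired test for bulging. Label it as added after results were known. If too few such controls exist for a useful comparison, report descriptively only. Keeping all 30 eTEP patients avoids discarding eligible patients merely because their matched control lacked documented diastasis.

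3. In the same case, reword 1.2.6, 1.2.8, the purpose in 1.2.12 and the conclusions to say that the control group was defined by procedure and not by diastasis. Limit comparative statements about patients with diastasis to the analysis in item 2.

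The cost is a check of 30 existing records and, if items 2 and 3 apply, one added analysis and changes of wording. The downsides are fewer controls and lower precision, partly broken matching, post hoc status, and possibly incomplete recording of diastasis in open-repair records, which could make the retained controls a selected subset.

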1.2.11 Exclusion Criteria

Group 1 (eTEP):

- Preoperative absence of midline abdominal wall hernias
- Preoperative absence of rectus abdominis diastasis
- Intraoperative performance of transverse abdominis release (TAR)
- Intraoperative inguinal hernia repair

Group 2 (Rives-Stoppa, control group):

- Intraoperative performance of transverse abdominis release (TAR)
- Intraoperative performance of anterior component separation
- Intraoperative inguinal hernia repair

1.2.12 Study Type

Single-center, observational study.

Non-randomized allocation:

- Group 1 (eTEP): First 30 patients who meet the inclusion criteria and do not exhibit any of the exclusion criteria will be investigated. The option for endoscopic eTEP repair, if feasible, is given preoperatively as a standard for the treatment of symptomatic midline abdominal wall hernias with concomitant rectus abdominis diastasis as an alternative to open Rives-Stoppa mesh repair. The modality of operative treatment is made in cooperation with the patient.
- Group 2 (Rives-Stoppa, control): Thirty patients will be selected out of all patients who underwent an open Rives-Stoppa (midline repair with sublay mesh) in our center and who do not meet any of the exclusion criteria. Patient selection will consist of matching to patients in group 1 according to gender and age (e.g. a male patient in group 1 will be matched to a male patient (group 2) out of our records

who underwent an open Rives-Stoppa repair and whose age most closely resembles the age of the matched patient in group 1).

Masking: None.

Assignment: Two-group, parallel.

Purpose: Comparing two routinely used interventions for the treatment of midline abdominal wall hernias with rectus abdominis diastasis.

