1.2.20 Summary of Results

Date of posting of results summaries: December 26, 2022 (within study protocol).

Date of the first journal publication of results: Not yet achieved.

[figure not shown]
URL: Not (yet) applicable.

Baseline characteristics:

- Group 1 (eTEP): EHS Registry: BEGZ, BEHA, BEHB, BEJR, BEJS, BEJT, BEJW, BEJX, BEJZ, BEKA, BEKB, BEKC, BEKG, BEKH, BEKI, BEKJ, BEKK, BEKK, BEKM, BELE, BELF, BELG, BELH, BELI, BELJ, BELK, BELL, BEOD, BETJ, BETK.
- Group 2 (Open RS): EHS Registry: BELN, BELO, BELQ, BELR, BELS, BELT, BELU, BELV, BELV, BELY, BEOF, BEOH, BEOO, BEPV, BEPX, BEPY, BEPZ, BEQA, BEQF, BEQG, BEQJ, BEQK, BEQQ, BEQR, BEQS, BEQT, BEQV, BEQX, BETN, BETO.

Participant flow (see also participant flowchart on next page):

Date	Group 1	Group 2
June 9, 2022	23 participants	23 participants
June 13, 2022	24 participants	24 participants
June 17, 2022	25 participants	25 participants
June 20, 2022	26 participants	26 participants
June 21, 2022	27 participants	27 participants
July 11, 2022	28 participants	28 participants
August 30, 2022	30 participants	30 participants

Adverse events:

- Three conversions were needed in group 1 (eTEP) because no adequate visualization could be achieved (1 participant) or because the diastasis was deemed to large to be appropriately closed endoscopically (2 participants)
- Observed complicationa according to the Clavien-Dindo (CD) classification [3]:
 During hospital stay in the eTEP group: 1x CD I, 12x CD II.

 During hospital stay in the Open RS group: 4x CD I, 10x CD II, 4x CD IIIb.

 After discharge until 30 days in the eTEP group: 5x CD I, 1x CD II, 2x CD IIIa, 1x CD IIIb.

 After discharge until 30 days in the Open RS group: 5x CD I, 1x CD II, 5x CD IIIa, 4x CD IIIb.

Outcome measures: See brief summary.

URL protocol files: Not applicable.

Brief summary:

- Median length of hospital stay was longer in the open RS group.
- Median duration of patient-controlled analgesia was longer in the open RS group.
- Switch to only oral analgesics took longer in the open RS group.
- No significant difference in 'comparable parameter'* for postoperatively administered analgesics irrespective of PCA between both groups.
- No significant difference between the presence of prescription opioids at discharge.
- Median duration of surgery (skin-to-skin time) was significantly shorter in the open RS group.
- Need for drainage (postoperative drain inserted during primary surgery) was significantly greater in the open RS group.

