2.1 Introduction

2.1.1 Background and Rationale:

Extended view totally extraperitoneal prosthesis (eTEP) repair is a fairly new, up-and-coming technique as a treatment option for ventral abdominal wall hernias. The endoscopic eTEP approach has been proven to be a feasible approach [4, 5]. Our center recently started offering this treatment option from September 7, 2021 (first performance of the eTEP surgery within our center) onwards as a minimally invasive alternative to an open Rives-Stoppa [6] repair. A quick search revealed some comparisons of eTEP with IPOM [7], or comparisons between robotic and endoscopic eTEP [8], but little or no information could be found about comparisons between endoscopic (non-robot-assisted) eTEP and open Rives-Stoppa repair. Since the endoscopic eTEP repair and the open Rives-Stoppa repair both consist of a retromuscular mesh placement, and the endoscopic eTEP procedure is offered as a minimally invasive alternative to an open Rives-Stoppa repair in our center, an objective comparison between the two of them seemed logical.

2.1.2 Objectives:

To compare the outcomes of endoscopic eTEP repair versus open Rives-Stoppa repair in terms of length of hospital stay, postoperative pain management and complications.

2.1.3 Trial Design:

Partially retrospective, partially prospective, two-group, parallel, observational, superiority cohort study with an allocation ratio of 1:1.

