3.1.3 Interventions

Explained under 1.2.9 and elaborated under 1.2.10, 1.2.11 and 1.2.12. All procedures were performed or will be performed by one of three surgeons listed under 1.5 as contributor 2, contributor 3 and contributor 4.

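### Group 1 is the centre's first 30 eligible eTEP cases, so the superiority comparison confounds technique with the centre's introduction of eTEP

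*Protocol*

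**What the plan says.** - **Who enters Group 1.** The source population in Protocol 1.2.10 is "Patients who underwent an eTEP procedure in our center", with midline hernia and rectus diastasis also required. The rule in 1.2.12 is "First 30 patients who meet the inclusion criteria and do not exhibit any of the exclusion criteria will be investigated". Neither section sets a start date, a run-in or a minimum number of prior cases.
- **When eTEP began.** Section 2.1.1 says that the technique "is a fairly new, up-and-coming technique as a treatment option for ventral abdominal wall hernias", and: "Our center recently started offering this treatment option from September 7, 2021 (first performance of the eTEP surgery within our center) onwards".
- **Who enters Group 2.** Section 1.2.12 draws 30 controls from all eligible open Rives-Stoppa patients in the centre's records, with no date window. They are matched on gender and nearest age, and not on surgeon or calendar period.
- **Who operated.** Section 3.1.3, for both groups: "All procedures were performed or will be performed by one of three surgeons listed under 1.5 as contributor 2, contributor 3 and contributor 4".
- **What is claimed.** Section 1.2.12 gives the purpose as "Comparing two routinely used interventions for the treatment of midline abdominal wall hernias with rectus abdominis diastasis". Section 2.1.2 sets out to compare the two repairs on length of stay, pain management and complications, and 2.1.3 calls the study a superiority cohort study. None of these limits the claim to an introduction phase.

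**The concern.** A centre's first cases of a technique differ from its later ones in ways unrelated to the technique's settled performance. Operators and theatre teams may be gaining experience, early patients may be chosen as more straightforward, and early patients may be kept in hospital longer as a precaution. Here the rule that defines Group 1 selects such a period, while nothing restricts the control pool in the same way. A difference between groups, or its absence, can then come from the technique, from the introduction period, or from both.

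At stake is how far the results in 1.2.20 reach. Some reported there are plausibly sensitive to experience: operating time ("Median duration of surgery (skin-to-skin time) was significantly shorter in the open RS group"), three conversions in Group 1, and midline bulging in 11 eTEP participants against none in the open group. Length of stay, a primary outcome, could be moved either way. If the conclusion is worded as eTEP versus open Rives-Stoppa in general, readers will apply it to centres and periods that the data do not cover.

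**Working it through.** **1. Does Group 1 start at the first eTEP?** The protocol does not say so outright. Three things point to it:
- Sections 1.2.10 and 1.2.12 take the first eligible patients among all eTEP patients at the centre, with no later start date.
- Section 3.1.7 allows inclusion after surgery, and the participant flow in 1.2.20 shows 23 patients already in Group 1 on 9 June 2022, the date of first enrolment (1.2.13).
- The pace of inclusion fits a count from 7 September 2021.

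Pace, with 30.44 days per month:
- 7 September 2021 to 9 June 2022: 275 days, 23 patients; 23 / 275 × 30.44 = 2.55 per month.
- 9 June 2022 to 30 August 2022: 82 days, 30 − 23 = 7 patients; 7 / 82 × 30.44 = 2.60 per month.
- Exact binomial test of 23 out of 30 against the time share 275 / 357: p = 1.0.

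With only 7 patients in the second window, this is consistency and not proof.

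**2. How long is the window?** 275 + 82 = 357 days from first eTEP to last inclusion. These are inclusion dates. Because 3.1.7 also allows inclusion at consultation before surgery, some operations could be later. The outer limit is the actual completion date, 23 December 2022 (1.2.19), which is 472 days after the first eTEP.

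**3. Conversions.** 3 / 30 = 10%, exact (Clopper-Pearson) 95% interval 2.1% to 26.5%. Section 1.2.20 gives one for inadequate visualization and two for a diastasis judged too large. Their place in the case sequence is not shown.

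**4. What could a shift of a given size do?** The protocol gives 30 per group without alpha, power, effect size or SD, so there is no planning figure to reproduce. The following is for scale only and assumes two-sided alpha 0.05 and a normally distributed outcome.
- Standard error of the difference in SD units: √(2 / 30) = 0.258.
- Difference detectable with 80% power: (1.960 + 0.842) × 0.258 = 0.72 SD.
- If the techniques were equal and the introduction period alone shifted the mean by s, the probability of a significant result is 1 − Φ(1.96 − s / 0.258) + Φ(−1.96 − s / 0.258).
- If eTEP truly had a 0.72 SD advantage and the shift worked against it, power is Φ((0.72 − s) / 0.258 − 1.96).

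| Assumed shift s (SD) | Significant although techniques are equal | Power for a true 0.72 SD advantage |
|---|---|---|
| 0 | 0.05 | 0.80 |
| 0.25 | 0.16 | 0.45 |
| 0.50 | 0.49 | 0.14 |
| 0.75 | 0.83 | not computed |

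Nothing in the protocol says which row applies, or that any shift occurred.

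**5. Can an analysis separate the two?** No. Every Group 1 patient belongs to the introduction series, so no later eTEP cases exist to compare. A trend by case number can describe the series but cannot remove the confounding from the between-group contrast.

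**The case against.** The protocol is open about the facts. It calls the technique new, dates the centre's first case and states the first-30 rule, so a careful reader can see that this is an early series. That stands, but disclosure in the background does not narrow the objective or the conclusion.

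Several stronger readings are tempting and are not supported:
- **That the stated purpose is false.** A reader might infer that calling both interventions routinely used contradicts 2.1.1. Sections 1.2.12 and 4.1.7 present eTEP as offered within standard care, and the phrase can fairly mean that. It need not claim operators past their learning phase.
- **That the summary attributes longer surgery to the technique.** Section 1.2.20 only describes the median by group.
- **That three surgeons shared the eTEP cases, about ten each.** Section 3.1.3 says each procedure in either group was done by one of three surgeons. It does not say that all three performed eTEP, and their experience elsewhere is not given.
- **That the reported advantages of eTEP are inflated.** Learning would usually work against the new technique, so the shorter stay and shorter PCA may be conservative. Easier early cases would act the other way, and no section shows which occurred.

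It is also fair that skin-to-skin time and conversion are not listed outcomes, that two of the three conversions may reflect anatomy or case selection, and that a case-order analysis could sit in an analysis plan or final report not shown here. The point therefore does not rest on a missing analysis. It rests on the selection rule and the objective, both fixed in the protocol.

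**Conclusion.** The point holds as a limit on what the study can conclude. By rule, Group 1 is the first 30 eligible eTEP patients at a centre that had just begun the procedure, and controls are drawn from all its open Rives-Stoppa records with matching on gender and age only. The superiority comparison in 2.1.2 and 2.1.3 therefore confounds technique with introduction, for all 30 of 30 Group 1 patients.

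This assumes that the count starts at the first eTEP, which is inferred. It is shown at centre level and not for individual surgeons. That open Rives-Stoppa was the settled practice is implied by eTEP being introduced as its alternative, but not stated. The size of any shift is unknown, as is its direction for length of stay. A reader might infer that the reported differences are learning effects, but the documents do not show that. This is a cheap improvement to the claim and the reporting, and it does not invalidate the data.

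**What to change.** 1. State in the conclusion and final report that the comparison is the centre's first 30 eligible eTEP cases versus its open Rives-Stoppa practice, and that it does not extend to eTEP after the introduction phase. Do this whether or not a trend is seen, because a flat trend in 30 patients would not restore the general claim.
2. If 1.2.12 and 2.1.2 are reworded to match, log the change as a dated clarification made after results were posted.
3. From the operation records, take each Group 1 patient's consecutive eTEP case number, overall and per surgeon. Count every eTEP since 7 September 2021, including operations that were ineligible for the study, since these also add experience.
4. Plot length of stay, analgesia duration, skin-to-skin time, conversion and complications against case number. Keep this descriptive, without formal tests on halves of 15.

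The cost is a few sentences and a retrieval of surgery date and operator, with no new patients. Journal publication had not been achieved at this protocol version (1.2.20), so the change can still be made. The downside is a narrower claim and an imprecise descriptive trend.
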